5.8.1.2 Criteria and methods for the premature termination of the research

- Any subject can withdraw from participating in the research at any time and for any reason.
- The investigator can temporarily or permanently end a subject's participation in the research for any reason that affects the subject's safety or which would be in the subject's best interests.
- In case of loss of follow-up, the investigator must try to contact the subject by any means possible in order to know at least if the patient is still alive, and report it in the patient's file.

If a subject leaves the research prematurely, data relating to the subject can be used unless an objection was recorded when the subject signed the consent form.

If consent is withdrawn, no data about the subject may be used unless the subject states in writing that he/she does not object. In practice, the subject is excluded from the research.

The case report form must list the various reasons for ending participation in the research:

- Ineffective
- Adverse reaction
- Other medical problem
- Subject's personal reasons
- Explicit withdrawal of consent

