5.3 End of research visit at 6 months

The end of research visit will be made at 6 months or when the patient terminates the study.

Primary outcome

The physician, physical therapist, research assistant or research nurse will collect blindly the mRS if the patient is alive. A face-to-face structured interview will be held during which the modified Rankin scale will be assessed (Appendix 1, 17).

Functional and cognitive status will be collected during the patient's consultation at 6 months, with using:

- SAHOT Score
- MOCA score
- Return to work
- Activities of Daily Living
- Instrumental Activities of Daily Living

The in-hospital morbidity indicators will be collected, including:

- Length of Intensive Care Unit stay
- Length of hospital stay

The occurrence of cerebral vasospasm and DCI during ICU stay will be assessed, with collecting

-Delayed cerebral ischemia, defined as the occurrence of focal neurological deficit or a decrease of at least 2 points on the Glasgow Coma Scale, which does not occur immediately after aneurysm occlusion and which is not ascribable to other causes.

[figure not shown]
-Cerebral artery vasospasm, defined as a reduction of the diameter of the proximal cerebral artery on either CT-, MR- or catheter angiography

-Cerebral infarcts, considered when detected on the CT scan or MRI performed with 6 weeks, (or on the latest CT scan or MRI performed before death within 6 weeks, or at autopsy), but not present on the earlier CT or MRI scan performed between 24 and 48 h after early aneurysm occlusion and not ascribable to other causes

5.4 Expected length of participation and description of the chronology and duration of the research.

Inclusion period	42 months
The included subjects' length of participation, of which:	

 • Treatment period: • Follow-up period: 	2 weeks 6 months
Total research period:	49 months

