5.8 Termination rules

5.8.1 Criteria and methods for prematurely terminating the research treatment

5.8.1.1 Different situations

- Temporary termination of treatment, the investigator must document the reason for stopping and restarting the treatment in the subject's source file and the case report form (CRF)
- Premature termination of treatment, but the subject is still included in the research, until the end of the subject's participation, the investigator must document the reason (if during the administration period, the patient get out of the ICU, the treatment will stop).
- Premature termination of treatment and end of participation in the research.

The investigator must:

- o Document the reason(s)
- o Collect the assessment criteria when participation in the research ends, if the subject agrees
- o In case of severe adverse event, subject will be closely monitored and followed.

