5.8.2 Follow-up of the subjects after the premature termination of treatment

Ending a subject's participation does not affect the normal management of the subject's illness in any way.

If there are serious adverse events, the investigator must notify the sponsor and monitor the subject for a month following the premature termination of treatment. If treatment is stopped prematurely due to a serious adverse event, a serious adverse event notification form will be sent by [contact]) to the sponsor. The serious adverse event will be monitored until it is resolved.

If a data and safety monitoring board (DSMB) has been created, this committee can specify and/or validate the monitoring methods.

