12.2.1 Primary Estimand – Intention-to-Treat (ITT) Analysis

This estimand aims to assess the effect of cilostazol added to nimodipine on the modified Rankin Scale (mRS) at 6 months, considering all randomized patients, regardless of intercurrent events.

- Target Population: All randomized patients.
- Variable of Interest: mRS at 6 months, dichotomized as favorable outcome (mRS 0-2) vs. unfavorable outcome (mRS 3-6).
- Handling of Intercurrent Events:
 - Early treatment discontinuation → "Treatment Policy" strategy: Patients remain in their randomized group, regardless of treatment adherence.
 - Death before 6 months → "Composite" strategy:
 - Neurological death → Counted as mRS=6.
 - Non-neurological death → Counted as mRS in ITT analysis and a secondary analysis excluding these patients.
 - Loss to follow-up → "Composite" strategy: Last observation carried forward (LOCF) with multiple imputation as a sensitivity analysis.
- Estimation Method: Logistic regression adjusted for age and initial severity (GCS grade) and centre.

◆ Justification: This approach respects the ITT principle, ensures comparability between groups, and provides a realistic assessment of treatment effect.

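### Sections 5.8.1 and 5.3 permit, without requiring, loss of the 6-month mRS in patients who stop study drug, which conflicts with the treatment-policy primary estimand

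*Protocol*

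**What the plan says.** Section 5.8.1.1 distinguishes three situations. The first is a temporary stop of treatment. The second is "Premature termination of treatment, but the subject is still included in the research, until the end of the subject's participation"; the only example attached to it is leaving the ICU during the treatment period. The third is "Premature termination of treatment and end of participation in the research". For the third, the investigator is told to "Collect the assessment criteria when participation in the research ends, if the subject agrees". Nothing says when the third situation applies in place of the second.

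Section 5.8.1.2 states that "The investigator can temporarily or permanently end a subject's participation in the research for any reason that affects the subject's safety", or where this would be in the patient's best interests. It continues: "The case report form must list the various reasons for ending participation in the research". That list has five entries: lack of effect, adverse reaction, other medical problem, personal reasons and explicit withdrawal of consent. The first three are thus separate from any refusal by the patient to be followed.

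Section 5.3, which contains the primary mRS interview, says "The end of research visit will be made at 6 months or when the patient terminates the study". After a treatment stop with a serious adverse event, section 5.8.2 asks the investigator to "monitor the subject for a month following the premature termination of treatment"; it does not mention the 6-month interview.

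On the analysis side, section 12.2.1 defines the variable as the dichotomised mRS at 6 months and applies a treatment-policy strategy to early discontinuation of treatment: "Patients remain in their randomized group, regardless of treatment adherence". Section 12.3 repeats this. For patients who exit before 6 months, 12.1 uses the last recorded mRS (that at ICU discharge), or non-response if none was recorded. Section 12.6 scores patients who leave early as non-responders.

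**The concern.** A treatment-policy strategy uses the outcome observed at 6 months whether or not the patient completed the 14-day course. It works only if patients who stop study drug are still interviewed at 6 months. The conduct sections do not secure this. They allow an event that bears on a short course of drug to close the patient's whole participation, and they allow the closing visit to stand at the time of exit. No other section asks for the 6-month mRS once participation has ended.

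The patients exposed to this gap are not a random subset. Sections 4.1.2 and 5.2 name arrhythmia, abnormal bleeding and allergy as major cilostazol-related events, and adverse reaction is a listed reason for leaving the research. Exits of this kind could be related to treatment. The substitute values are imputations: an mRS taken months early, or an assigned failure. Neither is the outcome that the estimand names, and no later analysis plan can recover an interview that was never held.

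**Working it through.** **Do the conduct sections deliver what the estimand needs?**

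1. The estimand needs the 6-month mRS in every randomised patient, including those who stopped drug (12.2.1, 12.3).
2. In the second situation of 5.8.1.1 the patient stays in, so the value can be obtained.
3. In the third situation the patient leaves. Assessment is then at exit and subject to agreement (5.8.1.1), and the final visit may take place at that time (5.3). The 6-month value is not requested.
4. Allocation to situation 2 or 3 is not governed by any rule. The reasons in 5.8.1.2 are given for ending participation and include three that concern drug effect or medical course.

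The conflict lies in step 3, and step 4 leaves its frequency open.

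**The plan's own design figures.** Inputs from section 12.5: response 0.65 and 0.76; looks at 95, 189 and 284 per arm; efficacy limits 3.7103, 2.5111 and 1.9308; binding futility limits at −0.2701, 1.1224 and 1.9308 (signs reversed so that a positive z favours cilostazol). Section 12.7 prints the second futility limit differently; the section 12.5 value is used.

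- Maximum information: 284 / (0.65×0.35 + 0.76×0.24) = 284 / 0.4099 = 692.85, as stated.
- Simulated power 0.80 and one-sided alpha 0.025, as stated.
- Inflation for 10% drop-out: 284 / 0.9 = 315.6, against 315 stated.

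With looks at 95/189/315 per arm and everyone followed, simulated power is 0.82.

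**Illustration of exits.** The protocol gives no exit rate for these reasons, so the rates d are assumed. Let k be the share of true responders among exits who keep a responder score: k = 0 is the non-responder rule of 12.6, and k = 0.5 supposes that carry-forward under 12.1 preserves half of them. Exits are assumed to have the same true response rate as their arm. The analysed rate is p × [1 − d(1 − k)].

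Example, 2% on placebo and 5% on cilostazol, k = 0: 0.65×0.98 = 0.637 and 0.76×0.95 = 0.722, a difference of 8.5 points instead of 11. With k = 0.5: 0.65×0.99 = 0.6435 and 0.76×0.975 = 0.741, a difference of 9.75 points.

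| Exits, placebo / cilostazol | Difference, k = 0 | Power, k = 0 | Difference, k = 0.5 | Power, k = 0.5 |
|---|---|---|---|---|
| 0 / 0 | 11.0 | 0.82 | 11.0 | 0.82 |
| 2% / 2% | 10.8 | 0.79 | 10.9 | 0.81 |
| 5% / 5% | 10.45 | 0.76 | 10.7 | 0.79 |
| 2% / 5% | 8.5 | 0.59 | 9.75 | 0.71 |

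In each row the estimated difference moves toward no effect. The 10% inflation does not offset this, because patients scored as failures remain in the denominator.

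**The case against.** A reader might infer that every patient with an adverse reaction leaves the trial and has no 6-month mRS. The text does not support that. The stay-in category exists, nothing obliges a site to end participation for an adverse reaction, and a site that uses the stay-in category collects exactly what the estimand needs. The loss is permitted, not automatic.

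A reader might also infer that the affected patients would mostly be counted as failures. That follows from 12.6 only. Under 12.1 it depends on the ICU-discharge mRS, whose distribution the protocol does not give. Nor is it right to measure the loss from the power of a single final test at 315 per arm: that ignores both interim looks and the binding futility limits, and the design's power is 0.80 at 284 or 0.82 at 315.

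Other safeguards count for something. A blinded mRS is taken at ICU discharge in case of loss to follow-up (5.2). Worst-case, multiple-imputation and complete-case analyses are planned (12.1, 12.4). Section 2.7 reports no difference in major adverse events between arms in earlier cilostazol trials in SAH, which argues against a large imbalance. In the scenarios shown, the bias does not favour cilostazol, so they raise no false-positive concern.

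These points limit the size and certainty of the problem. They do not remove it: none of the safeguards supplies an observed 6-month mRS, and the choice between the two categories is left without a criterion.

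**Conclusion.** The point holds as an inconsistency between the conduct sections (5.8.1.1, 5.8.1.2, 5.3) and the primary estimand (12.2.1, 12.3). The protocol permits loss of the 6-month mRS in patients who stop study drug for drug-related reasons, and then substitutes an earlier value or non-response. The planned sample size is not shown to be wrong; its figures reproduce.

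The number of patients affected cannot be derived from the documents. The power losses rest on assumed exit rates, on exits sharing their arm's true response rate, and on which of the two substitution rules applies, a matter on which 12.1 and 12.6 differ. With equal exits of 2–5% the loss is modest: 0.79–0.76 under non-response, or 0.81–0.79 if carry-forward keeps half of the true responders. It becomes material only if exits are more frequent on cilostazol: 0.59 or 0.71 at 5% against 2%. This is a cheap improvement worth making because the missing values cannot be recovered later.

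**What to change.** Reconcile 5.8.1.1, 5.8.1.2 and 5.3 with 12.2.1, without altering when or why study drug is stopped:

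- In 5.8.1.1 and 5.8.1.2, state that a patient whose study drug is stopped for any reason remains in follow-up to the 6-month mRS, unless the patient or proxy withdraws consent to follow-up.
- Split the CRF list into two: the reason study drug was stopped, and the reason follow-up ended.
- In 5.3, schedule the primary mRS at 6 months regardless of treatment status. Record any mRS taken at an early exit separately, with its date.

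The cost is protocol wording, one CRF split and some additional face-to-face visits at 6 months. Those visits are already planned for every patient. The patient's right to withdraw is unchanged.

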4.1 Concise description of the primary and secondary assessment criteria

4.1.1 Primary assessment criterion

Modified Rankin Scale (mRS) assessed at 6 months in a structured face-to-face interview. Favorable outcome is defined by an mRS score 0 to 2, and unfavorable outcome by a mRS from 3 to 6. (Appendix 1)

The Modified Rankin scale allows to score the functional state. It is the most widely used outcome in patients with SAH¹⁷. It can be passed in a face-to-face interview by physicians, physical therapists, a research assistant or research nurses. Its overall agreement is 81% ($\kappa=0.74$, $kw=0.91$) when structured interview is used and displays an excellent repeatability.

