5.2 Follow-up Visits

Follow up visits will be performed daily from day 1 to day 28. One Brain imaging will be realized 24/48 hours after the aneurism treatment and one between day 28 and 45 after randomization. Transcranial doppler, MR CTA or DSA results will be collected when realized.

Day 1 to day 28

Vital status

Compliance to treatment

Experimental Treatment administration will be collected daily

Safety follow up

- Any major Cilostazol-related adverse event will be assessed:
 - Arrhythmia from auricular origin
 - Arrhythmia from ventricular origin
 - Abnormal bleeding
 - Allergy
- Other minor Cilostazol-related adverse events:
 - Tachycardia,
 - Fever
 - Fainting
 - Nausea
 - Vomiting
 - Stomach pain

Cerebral vasospasm

- Blood flow velocity increase on TCD
- Cerebral vasospasm diagnosed upon MR/CTA or DSA and its severity (mild/moderate/severe)

Delayed cerebral ischemia

- New focal deficit
- Glasgow point decrease
- No other cause

Treatment in the last 24 hours

- Continuous sedation
- Mechanical ventilation
- Extraventricular drain
- Therapy Intensity Level (TIP) for Raised ICP treatment (See Appendix 7)
- Hypertension therapy
- Vasopressors (epinephrine/norepinephrine/dobutamine)
- Milrinone administration
- Endovascular treatment (Balloon therapy or vasodilatator administration)
- Other treatment
- At ICU discharge, the modified Rankin scale will be evaluated by a blinded research technician in case of lost to follow up.

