8 ASSESSMENT OF EFFICACY

8.1 Description of parameters for assessing efficacy

Primary outcome

It is the Modified Rankin score (mRS):

It will be assessed at 6 months by physicians, physical therapists or research assistant or research nurses who would have been specifically trained to pass this score and who will be unaware of the trial-group assignments, during a face-to-face interview with patient. This structured interview will strengthen the interrater agreement (17)

Methods for secondary assessment criterion collection

At the 6 months interview and after collection of the mRS, one will proceed to the assessment of

- The SAHOT score (Appendix 2). For facilitating its collection and reduce time of the consultation, the SAHOT questionnaire will be sent to the patients before the 6 months face-to-face interview.
- MOCA score at 6 months (Appendix 3), which will be passed during the 6 months face-to-face interview by the trained investigator.
- Return to work at 6 months
- Activities of Daily Living (ADL) at 6 months (Appendix 4) and Instrumental Activities of Daily Living (IADL) at 6 months (Appendix 5), which will be passed during the 6 months face-to-face interview by the trained investigator.

Radiological endpoints will be collected daily during the ICU stay. Delayed cerebral ischemia is defined in the section 4.1.2 Highest velocity in the mean cerebral artery evaluated in tCD will be collected when available. MR/CTA DSA vasospasm will be scored as mild, moderate or severe according to the narrowing of the cerebral arteries.

8.2 Anticipated methods and timetable for measuring, collecting and analysing the parameters for assessing efficacy

Efficacy will be assessed with help of the mRS at 6 months, during a structured face-to-face interview of the patients which will involve one of the physicians, physical therapists, research assistants or research nurses of any participating centre. The organisation of the structured "CASH" protocol, version 2.1 of 04/04/2025

face-to-face interview will be as similar as possible between centres. During this M6 visit, the secondary outcomes- related scores will also be collected:

- SAHOT
- MOCA score
- Activities of Daily Living
- Instrumental Activities of Daily Living
- Return to work

During hospital stay, other parameters evaluating efficacy will be prospectively collected and reported on the e-CRF:

- Length of stay in the ICU
- Length of hospital stay
- 28-day mortality

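### The 6-month mRS has no back-up mode of assessment, and tracing of lost patients must yield only vital status, so obtainable primary outcomes may be replaced by substitute values.

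*Protocol*

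**What the plan says.** On how the primary outcome is taken, the protocol is uniform:

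- Section 4.1.1 defines it as "Modified Rankin Scale (mRS) assessed at 6 months in a structured face-to-face interview".
- Section 5.3: "A face-to-face structured interview will be held during which the modified Rankin scale will be assessed".
- Section 8.1 has trained, blinded assessors rate it "during a face-to-face interview with patient". Section 8.2 adds that the assessor may belong to any participating centre.
- The synopsis and the care/research table in 5.7 list the same face-to-face interview.

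No telephone, video, home-visit or proxy route is named, and none is forbidden.

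On patients who do not reach the visit:

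- Section 5.8.1.2: "the investigator must try to contact the subject by any means possible in order to know at least if the patient is still alive".
- Section 5.8.1.1, when treatment and participation both end early: "Collect the assessment criteria when participation in the research ends, if the subject agrees". Section 5.3 likewise places the final visit at 6 months or when the patient leaves the study.
- Section 5.2: "At ICU discharge, the modified Rankin scale will be evaluated by a blinded research technician in case of lost to follow up".

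On a missing 6-month mRS, there are two rules. Sections 12.1 and 12.2.1 carry the ICU-discharge value forward, and 12.1 assigns non-response only when no mRS exists. Section 12.6 counts patients lost to follow-up as non-responders in the main analysis.

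**The concern.** The tracing rule already makes the site reach the patient or family by whatever route works. The protocol then requires nothing from that contact beyond vital status, and nothing in it says that an mRS taken remotely may be entered as the primary outcome. A site that follows 4.1.1, 5.3 and 8.1 to the letter would leave the field empty, while another might enter a telephone rating. Where it stays empty, the trial uses either a value taken months earlier in the acute phase or a fixed failure.

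This is a conduct rule for sites. A statistical analysis plan cannot recover a rating that nobody asked for. Section 12.6 itself recognises that a single late assessment exposes the trial to loss to follow-up. What is at stake is avoidable missingness in the primary endpoint, with some loss of power and a treatment effect estimated partly from substitutes.

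**Working it through.** **1. Reproduce the design.** Inputs from section 12.5: favourable rates 0.65 and 0.76; one-sided alpha 0.025; looks at 95/189/284 per arm; efficacy boundaries −3.7103, −2.5111, −1.9308; futility boundaries 0.2701, −1.1224, −1.9308. Simulation with a pooled z statistic gives power 0.80, against 0.8016 stated. Drop-out inflation: 568/0.9 = 631.1, so 632, against 630 stated. The design reproduces.

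**2. Express the substitution.** Let p be the true favourable rate in an arm and m the proportion lost, equal in both arms.

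- Losses scored as failures (12.6), with lost patients responding at r times the average rate and p held fixed: observed rate = p(1 − m·r).
- ICU-discharge value carried forward (12.1, 12.2.1), where a share q of lost true responders already had mRS ≤2 at ICU discharge and no true failure did: observed rate = p(1 − m(1 − q)).

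Both have the form p(1 − e), with e = m·r or e = m(1 − q). None of r, q and the share recoverable by another mode is in the documents.

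**3. Power with the printed boundaries, 315 per arm at the final look**

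| e | Observed rates | Difference (points) | Looks 95/189/315 | Looks 105/210/315 |
|---|---|---|---|---|
| 0 | 0.650 vs 0.760 | 11.0 | 0.82 | 0.84 |
| 0.02 | 0.637 vs 0.745 | 10.8 | 0.79 | 0.81 |
| 0.025 | 0.634 vs 0.741 | 10.7 | 0.79 | 0.81 |
| 0.05 | 0.618 vs 0.722 | 10.5 | 0.76 | 0.78 |
| 0.10 | 0.585 vs 0.684 | 9.9 | 0.69 | 0.71 |

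The first schedule keeps the planned interim numbers; the second spaces the looks in proportion to 315.

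**4. What recovering half of the losses is worth (10% to 5%)**

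- Scored as failures, average responders (r = 1): e goes from 0.10 to 0.05; power from 0.69–0.71 to 0.76–0.78, a gain of about 7 points.
- Scored as failures, half the average response (r = 0.5): e from 0.05 to 0.025; power from 0.76–0.78 to 0.79–0.81, about 3 points.
- Carried forward with q = 0.5: the same values of e, so again about 3 points.
- Scored as failures, no true responders among the lost (r = 0): e = 0 throughout, no gain.

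**5. Which patients the 10% covers.** Section 12.5 gives it as a ceiling on drop-out, and 5.8.3 as the estimated drop-out rate. In 12.6 it comes directly after the statement that patients who resign leave the primary analysis. To that extent it describes people whom a telephone call cannot recover.

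**The case against.** A reader might infer three stronger things, and the documents support none of them.

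- That sites ask traced patients only whether they are alive. The wording of 5.8.1.2 sets a floor, and 5.8.1.1 and 5.3 provide for collecting the outcome at early exit. Those provisions cover an agreed exit, though, and do not address a patient who stays in the trial but cannot come at 6 months.
- That a remote rating is prohibited. It is unstated. The gap is that sites are given no basis for accepting one and may differ.
- That such patients all become failures. That follows from 12.6 alone. Under 12.1 and 12.2.1 the blinded ICU-discharge rating, collected for this very case, is used first.

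The size is also open to challenge. It is natural to argue that those who cannot attend are the most disabled, but if so, scoring them as non-responders is mostly right and little power is lost. The 7-point gain requires lost patients to respond at average rates. The power loss also comes mainly from how missing outcomes are scored, so it should not be counted a second time against the interview mode.

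Finally, face to face is a reasoned choice. The protocol links the structured interview to rater agreement, the MOCA at the same visit includes drawing tasks, and the assessor may come from any participating centre, which eases distance. All of this supports keeping face to face as the default. None of it argues against a back-up for the mRS alone.

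**Conclusion.** The point holds as a gap. No fallback mode is specified for the primary outcome, and the tracing rule requires vital status without requiring the mRS. Outcomes that could be obtained may be replaced by an ICU-discharge value or by non-response, depending on which of two conflicting rules is applied.

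Its size cannot be fixed from the documents. With 10% loss halved to 5%, the gain runs from about 7 points of power (scored as failures, average responders) through about 3 points (half the average response, or carry-forward with half of lost responders already at mRS ≤2) to none if the lost are all true non-responders. Equal loss in both arms and the half-recovery rate are assumptions. Patients who withdraw consent are outside any gain. That non-attenders are more disabled or live further away is plausible but not documented. This is a cheap improvement worth making, not a flaw that invalidates the design.

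**What to change.** - In 4.1.1, 5.3, 8.1 and 8.2, keep face to face as the default. Add that, if the visit cannot take place, a blinded trained assessor completes the same structured mRS interview by telephone or video with the patient, or with a relative or carer, and records the mode and the respondent. The Appendix 1 questions are spoken, and several are phrased about the person, so they can be asked this way.
- In 5.8.1.2, require vital status and, where the person agrees, the structured mRS.
- Add a sensitivity analysis restricted to face-to-face ratings.
- Reconcile 12.1 and 12.2.1 with 12.6, so that one rule governs a 6-month mRS that is still missing.

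Cost: a few sentences, a CRF field or two, and one additional analysis, with no added visit. The downside is a possible difference between remote or proxy ratings and in-person ratings. The documents do not give its size; recording the mode and the restricted analysis would let it be examined.
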